**1. Introduction and Purpose:**

1. *Describe why this research project will be done. Clearly state the overall objectives, specific aims, hypotheses and rationale for performing the study.*

Preterm birth, defined as birth at less than 37 weeks, affects 11 - 13% of all births in the United States and results in significant morbidity and mortality for the approximately 500,000 infants born preterm each year. The leading cause of preterm birth is preterm labor, and obstetrical interventions have included various tocolytic medications. Efficacy studies on these have yielded disappointing results. (Leveno et al, 1986; Leveno et al 1990; Canadian Preterm Labor Investigators Group, 1992; Leveno and Cunningham, 1992, Mercer and Merlino, 2009). There has been recent interest in nifedipine as a tocolytic for preterm labor (Conde-Agudelo et al, 2011). In 2008, a survey of maternal-fetal medicine specialists reported that 32% were using nifedipine as their tocolytic of choice (Fox et al, 2008), despite that there are no placebo-controlled, randomized studies of nifedipine for acute tocolysis preterm labor showing a benefit.

This is a randomized, double-blinded, placebo-controlled trial of nifedipine for acute tocolysis of preterm labor. Our objective is to determine whether nifedipine decreases the rate of preterm birth. Our null hypothesis is that nifedipine does not reduce the rate of preterm birth.

2. *Indicate the Primary and Secondary Study Endpoints. Also indicate the Primary Safety Endpoints (unless the study is a safety study).*

The primary outcome will be prolongation of pregnancy until at least 37 weeks. Secondary outcomes will include 1) number of patients who receive at least 2 doses of betamethasone, 2) delivery within 48 hours of diagnosis of preterm labor and 3) delivery within 7 days.

3. *Explain why the study risks are reasonable in relation to the potential benefits to subjects and society.*

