#### **4. Study Procedures:**

- 1. Provide a chronological description of all study procedures. If applicable, divide procedures into pilot, screening, and procedures performed at each regular visit. Indicate how many total visits and approximately how long visits will last. For studies that are providing medication(s), give the name(s), dosage, and route of administration. For studies that have more than one arm/part, provide the above information for each.*

Women presenting with symptoms of preterm labor will be assessed using electronic external fetal heart rate and uterine contraction monitoring. Women will receive a baseline and subsequent cervical exams as necessary. If at any time during her evaluation, the woman is dilated to at least 2 cm and has uterine contractions, she will be potentially eligible for study. Women with a singleton gestation between 28-0/7 weeks and 33-6/7 will be approached for consent to participate by Research Nurses employed by the Department of Obstetrics & Gynecology or [name] if a Research Nurse is unavailable. They will be randomized by the IDS Pharmacy into treatment (study drug, nifedipine) or control (placebo) groups.

Study women will receive nifedipine 20 mg or placebo oral capsule followed by a second dose after 90 minutes if there are persistent contractions. Four hours after the initial dose, they will begin nifedipine 20 mg or placebo oral capsule every 4 hours for a total duration of 48 hours, up to a maximum of 160 mg the first 24 hour period (120 mg the second 24 hour period), unless delivery occurs sooner. We anticipate that women will remain on Labor & Delivery for monitoring for at least 24 hours prior to consideration of transfer to the high-risk antepartum unit.

There will be a "HOLD DOSE" parameter in which a dose will be held if an enrolled patient:

- refuses medication
- has heart rate greater than 120

If a dose is held, the nurse will contact the 4th year resident who will ensure [name] is notified.

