## **6. Criteria for Inclusion of Subjects:**

1. *Describe the characteristics of the subject population. For example, list any characteristics required for eligibility, such as diagnosis, prior therapy, age, or gender.*

Inclusion criteria include:

- Mothers between 16 and 44 years of age inclusive.
- Singleton pregnancy
- Intact membranes
- Between 28-0/7 weeks and 33-6/7 weeks' gestation inclusive
- Reported or documented uterine activity
- Cervical dilation between 2 cm and 4 cm inclusive

2. *Explain the rationale for the use of special classes of subjects who are more likely to be vulnerable, such as pregnant women, children, cognitively impaired people or prisoners.*

Pregnant women are included as this study is for an intervention for preterm labor.

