### **Summary of Sections 66.0 and 67.0 of the Smart Form for the Data Safety Monitoring Plan and Committee**

*Who comprises the Data Safety Monitoring Committee (DSMC)?*

The DSMC is composed of [name], PhD, Professor and Statistician within the Department of Obstetrics and Gynecology, as well as two faculty physicians from the Department of Obstetrics and Gynecology not participating in the study ([name] and [name]).

*When will the DSMC meet:*

The DSMC will meet at least annually during the projected 4 year duration of the study. Additionally, after accrual of 75 patients (half of the planned 150 patients for recruitment), an interim analysis will be performed.

*What will be analyzed by the DSMC?*

The DSMC will monitor study accrual rate, study attrition including participant withdrawals/dropouts, patterns of AEs and/or unanticipated events, patterns of protocol deviations and/or violations and changes in risk/benefit. Efficacy (positive and negative) as well as possible futility of further study will be examined at the interim analysis. Significance levels for the interim analysis will be altered by the method of Lan-DeMets. Safety will be evaluated at each meeting of the Data Safety and Monitoring Board.

*How will safety be evaluated and what study-specific stopping rules will be used by the DSMC?*

Safety will be evaluated by analyzing situations in which administration of the study drug is stopped according to the "STOPPING RULE" below.

The study would be stopped if nifedipine is found to significantly delay preterm birth, or if a significantly greater number of stillbirths or emergency deliveries due to nonreassuring fetal heart tracing attributable to study drug during the 48 hour period during which the study drug will be administered for acute tocolysis of preterm labor.

*What safety mechanisms are built into the Nifedipine study protocol?*

Apart from the strict inclusion and exclusion criteria and the plan to continue maternal and fetal monitoring for at least 24 hours after beginning the study, the following safety parameters are part of the study protocol:

There will be a "HOLD DOSE" parameter in which a dose will be held if an enrolled patient either refuses medication or has a heart rate greater than 120. If a dose is held, the nurse will contact the 4th year resident who will ensure [name] is notified.

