## **13. Potential Benefits:**

1. *Describe the potential benefits of the research to the subjects, to others with similar problems, and to society. If there is no prospect of direct benefit to the subjects, state how the knowledge to be gained will benefit society enough to justify any risks to subjects.*

Potential direct benefits to the study participant are prolongation of pregnancy and avoidance of preterm birth. Potential benefits to society include a better understanding of whether nifedipine is an effective intervention for tocolysis of preterm labor.

**14. Biostatistics:** (omit this section for peer-reviewed research such as cooperative group, or NIH-sponsored studies, and for industry-sponsored research which has been submitted to FDA)

1. *Describe the statistical methods to be used to answer the study question(s). Pilot studies also require a method of analysis, but the justification of the target sample size is not required.*

T-tests (two-sided) will be used for continuous variables and Chi-squared tests for categorical variables. Power will be 80% and an alpha of 0.05 will be used.

2. *Explain how the target sample size was determined.*

Previous studies done on preterm patients at Parkland Hospital include Leveno et al (1986), Cox and Leveno (1990) and Chao et al (2011). In Chao et al (2011), there were 153 patients in 12 months. Over 4 years, we would anticipate four-times that ( $153 \times 4 = 612$ ). In Chao et al (2011, The Diagnosis and Natural History of False Preterm Labor, Obstet Gynecol), 27% of the patients diagnosed with contractions and with cervical dilation of less than 2 cm delivered prior to 37 weeks' gestation. However, this study by Chao et al was not a prospective study. Additionally, it focused on women with cervical dilatation less than 2 cm, whereas the current study includes women with cervical dilation of 2 to 4 cm dilated. Importantly, women with more cervical dilation are more likely to deliver early, and it is appropriate to revise the target enrollment.

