Fortunately, 2 prior Randomized, (placebo) Controlled Trials (RCT) of tocolysis (magnesium and ritodrine) from Parkland Hospital have been published. For the RCT by Leveno et al of ritodrine versus placebo (“Single-Centre Randomised Trial of Ritodrine Hydrochloride for Preterm Labour”, Lancet, 1986) in which women with singleton pregnancies and preterm labor with cervical dilation up to 4 cm, 39 of 52 (75%) patients randomized to the control group delivered between 27 and 35 completed weeks. Similarly, for the RCT of magnesium sulfate versus placebo by Cox and Leveno (“Randomized investigation of magnesium sulfate for prevention of preterm birth” Am J Obstet Gynecol 1990) in which women with singleton pregnancies and preterm labor with cervical dilation less than 5 cm, 55 of 80 (68.8%) of patients randomized to the control group delivered between 27 and 35 completed weeks’ gestation. These are important data derived from randomized, placebo-controlled, prospective trials done here at Parkland Hospital and we feel that our sample size should incorporate this prospectively obtained data. An average of the above preterm birth rates for these two RCTs at Parkland Hospital is 71.2% (39+55 / 52+80). In slight distinction to the above studies, for the current study, we are including women beginning at 28 weeks’ gestation, and we will be assessing preterm birth as delivery at less than 37 weeks. In theory, the preterm labor rate for delivery at less than 37 weeks (the primary outcome of the current trial) would be higher than this average preterm birth rate for women prior to 35 completed weeks’ gestation. However, using these prospectively obtained numbers from past studies of preterm labor at Parkland hospital, we would need approximately 150 women (75 women in each of the 2 arms) in order to detect a 1/3 reduction (from 71.2% to 47.5%) in the rate of preterm birth with 80% power and an alpha of 5%.

Analysis of internal obstetrics operations data indicates that for the month of March 2015, there were 10 women between 28-0/7 weeks and 33-6/7 weeks with preterm labor and a cervix of 2 to 4 cm dilation. Of these 10 women, 6 were ineligible for participation in the study (2 had diabetes in pregnancy, 1 women had a twin gestation, 1 women was only 15 years of age and 1 woman had bleeding concerning for abruption). Of the 4 eligible women in March of 2015, 2 elected to participate in the study, consistent with our ongoing consent rate of approximately 50%.

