Effective September 17, 2015, there has been a protocol change at the level of the Division of Maternal-Fetal Medicine at Parkland Hospital. This protocol change will be to give corticosteroids for fetal lung maturity to women with diabetes and to all women with hypertension who are at risk of preterm birth. This MFM Division level protocol change will affect this study of women at risk of preterm birth.

Given that 2 of the formerly ineligible women (due to diabetes) who presented in March 2015 would now be eligible due to the above protocol change, we estimate that up to 24 additional women (2 x 12 = 24) would be screened per year, and up to 12 additional women (50% of the 24 additional screened) would participate. Given that there were 29 women recruited over the initial 13 months (which equates to approximately 27 over 12 months), under the new practice in which corticosteroids will be given more broadly (and women with diabetes and mild hypertension not treated with medications are eligible for participation), we estimate that up to 78-90 women would now be screened, and of these, we estimate that 39-40 women would participate per year.

Therefore, over ~4-5 years, we would expect 300 patients screened and 150 patients consented. In order to detect a 33% reduction in the rate of preterm birth less than 37 weeks’ gestation, assuming 80% power and a 2-sided alpha of 5%, a sample size of 75 patients per arm (two arms, study drug and placebo), 150 patients total, will need to be recruited. So far in the current study, we have had about a 50% consent rate. Assuming a 50% recruiting rate (50% x 300 = 150), it is estimated that this study will take 4 to 5 years to complete.

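### The unadjusted chi-squared test is valid but ignores gestational age and dilatation at entry; pre-specified adjustment offers a modest, assumption-dependent gain at the same N

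*Combined protocol and SAP*

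**What the plan says.** Section 14 item 1 names the methods in one sentence: "T-tests (two-sided) will be used for continuous variables and Chi-squared tests for categorical variables". It adds 80% power and an alpha of 0.05; item 2 makes the alpha two-sided. No covariate, adjusted model or stratified test appears anywhere in the document.

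On allocation, Section 4 item 1 says "They will be randomized by the IDS Pharmacy into treatment (study drug, nifedipine) or control (placebo) groups". No stratification factor is described.

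Sections 6 and 7 fix the entry window at 28-0/7 to 33-6/7 weeks, and Section 6 requires "Cervical dilation between 2 cm and 4 cm inclusive". Both values must therefore be known before randomisation.

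Section 14 item 2 twice uses prognosis to argue about the planning rate. It sets aside an earlier cohort with less than 2 cm dilatation because "women with more cervical dilation are more likely to deliver early". It also reasons that the rate of delivery before 37 weeks "would be higher than this average preterm birth rate for women prior to 35 completed weeks".

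The data safety monitoring summary in Section 11 plans an interim look after 75 women: "Significance levels for the interim analysis will be altered by the method of Lan-DeMets". The spending function is not named.

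**The concern.** The outcome has a fixed end point, so gestational age at entry sets how long each woman is at risk. From 28-0/7 to 37-0/7 is 9 weeks; from 33-6/7 to 37-0/7 is 3 weeks and 1 day. The plan also says that dilatation matters for early delivery. An analysis that ignores both leaves explainable variation in the standard error.

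Precision is at stake, not validity. The chi-squared standard error already allows for chance imbalance between the arms. But recruitment is slow ("there were 29 women recruited over the initial 13 months", with 4 to 5 years projected), so precision that needs no extra women is worth having. The choice also has to be made in advance, because covariate adjustment chosen after seeing results by arm is open to challenge.

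**Working it through.** **Inputs from the documents (Section 14 item 2).** Control rate 94/132 = 71.2%; treated rate 47.5%; difference d = 0.237; two-sided alpha 0.05; power 80%; 75 per arm.

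**Step 1: reproduce the sample size.** The mean rate is 0.5935.
- 2 × 0.5935 × 0.4065 = 0.4825, square root 0.6946.
- 0.712 × 0.288 + 0.475 × 0.525 = 0.4544, square root 0.6741.
- Uncorrected n = (1.960 × 0.6946 + 0.8416 × 0.6741)² / 0.237² = 66.2 per arm.
- With continuity correction, n = (66.2/4) × [1 + √(1 + 4/(66.2 × 0.237))]² = 74.4, rounded up to 75. This matches the plan.

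**Step 2: power and precision at 75 per arm, unadjusted.**
- Standard error of the difference = √(0.4544/75) = 0.078. Half-width = 1.96 × 0.078 = 15.3 points.
- Formula power is 84.7% uncorrected and 80.3% with continuity correction. Exact binomial power is 85.8% and 81.7%.
- The comparisons below use the uncorrected test throughout, so dropping the correction is not counted as a gain.

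**Step 3: the gain by formula.** If the covariates explain a share R² of the outcome variance, the effective n per arm is 75/(1 − R²). The documents give no R², so a range is shown.

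| Assumed R² | Effective n per arm | Power |
|---|---|---|
| 0 | 75.0 | 84.7% |
| 0.02 | 76.5 | 85.5% |
| 0.05 | 78.9 | 86.5% |
| 0.10 | 83.3 | 88.3% |
| 0.20 | 93.8 | 91.7% |

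**Step 4: the gain by simulation (150 women, 20,000 replicates per cell).** These assumptions are not in the documents: gestational age uniform by day over the entry window; dilatation of 2, 3 and 4 cm in 50%, 30% and 20%; Weibull time to delivery with shape 1.0 (constant hazard), 0.7 or 0.5 (deliveries clustered early); hazard ratio per cm from 1.0 to 2.0. The adjusted analysis is the standardised risk difference from a logistic model. Variance ratios are adjusted over crude.

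| | HR 1.0 | HR 1.3 | HR 1.6 | HR 2.0 |
|---|---|---|---|---|
| Variance ratio, shape 1.0 | 0.964 | 0.946 | 0.910 | 0.857 |
| Variance ratio, shape 0.7 | 0.990 | 0.970 | 0.928 | 0.873 |
| Variance ratio, shape 0.5 | 1.002 | 0.976 | 0.936 | 0.880 |
| Adjusted power, shape 1.0 | 0.864 | 0.868 | 0.880 | 0.894 |
| Adjusted power, shape 0.5 | 0.851 | 0.856 | 0.870 | 0.894 |

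- Chi-squared power was 0.855 to 0.862.
- Other dilatation mixes (even thirds; 70/20/10%; 10,000 replicates) gave variance ratios of 0.833 to 0.987 and adjusted power of 0.851 to 0.909. At the best ratio the half-width is 15.3 × √0.833 = 14.0 points.
- Gestational age alone gave variance ratios of 0.956 to 0.971 (shape 1.0) and 0.993 to 0.998 (shape 0.5). Power changed by -0.8 to +0.6 point.
- With neither covariate prognostic, power fell from 0.861 to 0.848.
- Type I error at 60% in both arms was 0.048 to 0.054 adjusted and 0.053 to 0.057 for chi-squared.

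**Step 5: a separate simulation** (dilatation mix 40/35/25%, logistic outcome model, 8,000 runs per power scenario). Power, chi-squared versus adjusted, was 86.4% v 86.0% at R² = 0, 85.5% v 87.2% at about 0.06–0.07, 86.5% v 89.0% at about 0.10–0.12, and 85.3% v 91.1% at about 0.17–0.20. With large-sample standard errors, adjusted type I error reached 5.6% (simulation error about 0.3 point), which favours a small-sample reference distribution.

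**Step 6: chance imbalance.** Over 42 equally likely days the SD is √((42² − 1)/12) = 12.1 days, or 1.73 weeks. The SD of the difference in arm means is 1.73 × √(2/75) = 0.28 week. An imbalance of that size moves the crude difference by 0.9 to 1.7 points, small against a standard error of 7.8.

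**Step 7: the interim look.** Assuming O'Brien-Fleming-type spending (interim p < 0.0031, final p < 0.0490), overall adjusted type I error was 0.049 to 0.053. Power was 0.845 to 0.898 adjusted, against 0.853 to 0.856 for chi-squared. The model never failed at 75 women.

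**Step 8: sparse secondary outcomes**, a possibility for "delivery within 48 hours of diagnosis of preterm labor". With 150 women the adjusted model failed in 24% of simulated trials at a 3% event rate, 6% at 5% and 0.2% at 10%. It never failed with at least 15 events.

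**The case against.** The plan contains no mistake. The planned test holds its level, and at 75 per arm it exceeds the 80% target with or without continuity correction. A simple valid test is a defensible choice, and every figure for the gain rests on assumed inputs. At a hazard ratio of 1.3 per cm in the main set, adjusted power is 0.856 to 0.868 against 0.855 to 0.862 crude, which is close to nothing. The largest gain needs a hazard ratio of 2.0 per cm, a fourfold hazard between 2 and 4 cm, with women spread evenly over that range.

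The documentary support is also indirect. The dilatation statement compares 2–4 cm with under 2 cm and says nothing about strength within 2–4 cm. The argument about 35 versus 37 weeks concerns the outcome cut-off, not gestational age at entry. Silence on stratification does not prove there is none. Section 4 allows several cervical exams, so the value to be used has to be defined, and the document does not show that it reaches the analysis dataset.

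Most of this stands, and it limits the size and urgency of the point. It does not remove it. Time at risk to 37 weeks follows from the entry window itself, both values must be established for eligibility, and the likely loss is about 1 point. The definitional gaps can be closed in the wording of the change.

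**Conclusion.** The concern holds as a matter of efficiency. Neither the validity of the chi-squared test nor the sample size of 150 is in question. In the main simulations, adjusting for both variables changes the variance by between nil and a 14% reduction (17% with dilatation spread evenly) and power by -1 to +4.6 points. Most of any gain would come from dilatation; gestational age alone contributes little.

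These sizes depend on the assumed distribution of entry values, the timing of deliveries and the strength of dilatation within 2–4 cm. Confidence in the size of the gain is therefore moderate at best, and it may be nil. The change is worth making because it is cheap and its downside is small, but the trial is sound without it.

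**What to change.** In Section 14, before any unblinded look:

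- Make the primary analysis a logistic regression of delivery before 37 weeks on arm, gestational age at randomisation (days, linear) and dilatation (cm).
- Define dilatation as the last value recorded before randomisation. State how ranges and half-centimetres are coded and how a missing value is handled, without reference to arm or outcome.
- Report the standardised (marginal) risk difference and risk ratio with robust 95% confidence intervals and a t reference. This keeps the planned 71.2% versus 47.5% contrast; an adjusted odds ratio would not.
- Keep the chi-squared test as a sensitivity analysis, and as the fallback if the model does not converge.
- Use the same adjusted statistic at the Lan-DeMets interim analysis.
- Adjust a secondary binary outcome only if pooled, blinded counts show at least 15 events and 15 non-events. Otherwise report the crude difference with a 95% confidence interval.

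The cost is one paragraph in Section 14, one line for the interim analysis, slightly more analysis work, and about 1 power point if the covariates are not prognostic. N and visits do not change. No new measurement is needed, but confirm that both entry values reach the analysis dataset. The last enrolment count given, 29 women, is below the 75-woman look, so on the documents' figures the change could still be made in time.
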